#### 4.2 Study Population

Advertisements (Appendix 2) will be placed at University of Toronto downtown campus to invite volunteers who are interested to participate. All study participants will undergo informed consent process, prior to enrollment in the study. Categorization of participants and sites will be based on the clinical assessments. Other than the study-related oral health history recorded, there is no intention to obtain information from the participants" other dental or medical records. Sixty (60) qualifying volunteers that agree to participate and sign all corresponding forms will be enrolled.

The first participant will be assigned a number, and all the following enrolled participants will be assigned consecutive numbers by accession. The following inclusion and exclusion criteria will be utilized in this study.

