# 6. STUDY PROCEDURES

# 6.1 Randomized Assignment and Product Blinding

Qualified study participants will be randomly assigned to one of two study groups, either Group A or Group B, using randomization software. To maintain blinding, the manufacturer will produce both probiotics and placebo lozenges, dispense them in identical, opaque bottles, and label them as either Group A or Group B. The assignment of probiotics to one of these groups will be determined by the manufacturer and disclosed only at the study's conclusion. Each bottle will be labeled with a code (either letter A or B, followed by a number) and emergency contact information. The products will be distributed in sealed boxes that look identical to prevent any differences in appearance or packaging between study groups. Each product inside the box will be overwrapped and include instructions for at-home use and safety information, including emergency contact details.

To monitor study participant compliance, the investigators will use a pharmaceutical scale to ensure the number of lozenges remaining in the bottle matches the expected count at each study visit. A scale will be used to avoid the operator from seeing the lozenges, in order to preserve blindness in this study (placebo and probiotic lozenges are not perfectly identical).

Study participants will be assigned a unique identification number in chronological order (e.g., from 1 to 60) as they enroll in the study. These identification numbers have been pre-assigned to a study group based on a computer-generated randomization list provided by an independent statistician. Cohabitant study participants will be assigned to the same study group and receive the same products. Study participants will be instructed to avoid using any other oral hygiene products. There will be no dietary restrictions during the study.

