# 8.0 STATISICAL ANALYSES

Correlations between tissue and blood neutrophil subsets and standard periodontal disease parameters from oral exam will be assessed. Data will be complied in SPSS version 20. Changes in the clinical parameters of experimental gingivitis such as bleeding on probing, gingival index, plaque index and probing depths during day 0, 7, 14, 21, 28 and 35 will be compared using one-way analysis of variance (ANOVA) followed by Tukey multiple comparison.

Oral neutrophil counts as well as neutrophil subset formation during day 0, 7, 14, 21, 28 and 35 in oral rinse samples as well as blood samples will be compared using one-way analysis of variance (ANOVA) followed by Tukey multiple comparison.

Multiple sites within each study participant will be evaluated using a Gingival Bleeding Index (BOP) at baseline and 3-week post product use exams. The gingivitis bleeding scores will be averaged to provide a mean score per study participant for each exam period. Product means and standard deviations will be calculated for each time period. Analysis of Variance techniques (possibly including Analysis of Covariance using the baseline scores as the covariant) will be used to compare the difference between the two test treatments using the 95% confidence level ( $p \le 0.05$ ). The correlation of baseline to post-treatment results will be assessed graphically. If there is evidence of correlation, the baseline result will be included in the ANOVA model to adjust for baseline differences.

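### Cohabitants are allocated together, but the between-treatment analysis has no household term; if correlated pairs enrol, its standard errors will be somewhat too small

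*Protocol*

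**What the plan says.** Section 6.1 begins with individual randomisation: "Qualified study participants will be randomly assigned to one of two study groups, either Group A or Group B, using randomization software". The mechanism is a list tied to consecutive identification numbers: "These identification numbers have been pre-assigned to a study group based on a computer-generated randomization list provided by an independent statistician". The same paragraph then adds the household rule: "Cohabitant study participants will be assigned to the same study group and receive the same products". It does not say whose list entry governs when a second household member's next number points to the other group.

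The eligibility criteria (sections 4.3 and 4.4) neither exclude nor limit cohabitants. Section 4.2 recruits by advertisement on one university campus and sets the size: "Sixty (60) qualifying volunteers that agree to participate and sign all corresponding forms will be enrolled".

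Section 8.0 reduces the bleeding data to one value per person: "The gingivitis bleeding scores will be averaged to provide a mean score per study participant for each exam period". The treatments are then compared by "Analysis of Variance techniques (possibly including Analysis of Covariance using the baseline scores as the covariant"), which "will be used to compare the difference between the two test treatments using the 95% confidence level". Baseline enters the model if a graph suggests that it is correlated with the outcome. No household term, mixed model or clustered variance is mentioned.

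**The concern.** An ordinary ANOVA or ANCOVA on participant scores treats the 60 scores as independent given the arm. The household rule breaks this in one specific way: people who may resemble each other are always placed in the same arm, never split. Any positive correlation between them then adds to the variance of each arm mean, and the residual mean square does not pick it up. The error goes in one direction only: p-values too small and confidence intervals too narrow.

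The protocol gives reason to take the case seriously. It foresees cohabitants by writing a rule for them. Section 6.1 leaves diet unrestricted, so a shared household diet could plausibly act on gingival outcomes, although the document does not assert such a correlation.

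There is also a practical side. Section 12 sends the data to the sponsor for statistical analysis, and section 12.11 keeps documents that identify participants by name at the site. The mailing address is on the Personal Information Form (Appendix 4). Unless a coded household number is recorded, the analyst may be unable to tell who lives with whom.

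**Working it through.** **Inputs from the protocol.** 60 participants (section 4.2); one score per participant and a significance level of 0.05 (section 8.0).

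**Assumptions, because the protocol is silent.** Equal arms of n = 30; a two-sided test; households of at most two participants; pairs divided about evenly between arms; p pairs in total; within-household correlation ICC. The protocol gives no effect size, standard deviation or power, so it has no figure of its own to reproduce for this point.

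**Step 1: variance of an arm mean.** Let f = 2p/60 be the share of participants living with another participant. Relative to independence, the variance is multiplied by

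DE = 1 + f × ICC,

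the effective sample size is 60/DE, and the true standard error grows by √DE.

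**Step 2: what the ordinary analysis estimates.** The expected residual variance is slightly too low, by the factor 1 − f × ICC/29. The ratio of the reported to the true standard error is therefore about

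r = √[(1 − f × ICC/29) / DE].

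**Step 3: true type I error.** The critical value for 58 degrees of freedom is 2.002, so the true error is about 2 × P(T₅₈ > 2.002 × r).

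**Worked case, 10 pairs and ICC 0.4.** f = 20/60 = 0.333. DE = 1 + 0.333 × 0.4 = 1.133. Effective n = 60/1.133 = 52.9. r = √[(1 − 0.1333/29)/1.1333] = √(0.9954/1.1333) = 0.937. 2.002 × 0.937 = 1.876, and 2 × P(T₅₈ > 1.876) = 0.066.

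| Pairs | ICC | f | DE | Effective n | True SE larger by | Type I error, formula | Type I error, simulated |
|---|---|---|---|---|---|---|---|
| 0 | any | 0 | 1 | 60 | 0% | 5.0% | – |
| 1 | 0.2 | 0.033 | 1.007 | 59.6 | 0.3% | 5.1% | 5.1% |
| 4 | 0.2 | 0.133 | 1.027 | 58.4 | 1.3% | 5.3% | 5.3% |
| 10 | 0.4 | 0.333 | 1.133 | 52.9 | 6.5% | 6.6% | 6.6% |
| 14 | 0.6 | 0.467 | 1.280 | 46.9 | 13% | 8.4% | 8.3% |

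The simulated column uses 200,000 trials per setting with an ordinary two-group t-test. The last row is a stress case: it needs 28 of 60 participants (47%) to live with another participant, together with a high correlation.

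**The case against.** The strongest reply is that this may never matter. Without cohabitants, or without correlation, nothing is wrong, and with a handful of pairs the error rate hardly moves. That stands, and it is why the point is conditional. One-campus recruitment makes some pairs plausible; it does not make it plausible that nearly half the trial is paired.

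A second reply is that section 8.0 names an open family of methods, and that an analysis plan not shown here could add a household term. It could. But the protocol itself fixes both the allocation rule and the unit of analysis, and the two do not match. A later plan can also use households only if they were coded at enrolment.

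A third reply is that the rule has a sensible purpose, since it avoids product swapping and cross-contamination with a live organism between people who share a home. The protocol does not give this reason, but it is a good one, and nothing here argues against the rule.

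Three stronger readings are tempting and are not supported:

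- **Later household members are not randomised.** If the first member's list entry governs, the household is a randomised cluster and the later member is validly allocated with it. What is missing is the sentence saying so.
- **Knowing the letter in advance opens the trial to selection.** A second member's group letter is foreseeable, but section 6.1 leaves the meaning of the letters with the manufacturer until the end, and both members must meet the same eligibility criteria. The risk is limited.
- **Microbiome results suffer most.** Section 8.0 names no between-arm microbiome test, so there is no stated interval or p-value to which this could apply.

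**Conclusion.** The mismatch between allocation and analysis is real, and under positive within-household correlation it is always anti-conservative. Its size is unknown and probably small: about 0.1 to 0.3 percentage points of type I error with one to four pairs at ICC 0.2, and about 1.6 points with ten pairs at ICC 0.4. These figures rest on assumed pair counts and correlations, equal arms and a two-sided test. Figures above 8% should not be read as a forecast. The point is worth acting on because the remedy is cheap now, while the household code may be hard to recover once the data have been de-identified and transferred.

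**What to change.** Four changes:

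1. In section 6.1, state that the list entry of the first-enrolled member allocates the whole household, and how a later member's own number is then handled.
2. Add a coded household number to the participant assignment log, so that it reaches the analyst without names or addresses.
3. In section 8.0, use household-clustered standard errors in the between-arm comparisons, or a household random intercept where it can be estimated. With only a few pairs the intercept variance may be estimated at zero, so clustered errors are the safer default. If nobody cohabits, the ordinary analysis stands.
4. Add one sensitivity analysis limited to the first-enrolled member of each household. It keeps 60 minus the number of pairs: 56 participants with four pairs, 50 with ten.

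The cost is one data field, one change to the variance estimate and slightly wider intervals: in the settings above the true standard error is 0.3% to 1.3% larger with one to four pairs, and 6.5% larger with ten.

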# 6.2 Product Dispensing and Use at Home

Study participants will be instructed to brush their teeth twice daily (morning and evening) for two minutes each time with a toothpaste provided by the study and toothbrush and floss. The participants will be informed as to when home oral hygiene should be performed and the times they will be instructed to refrain from using oral hygiene products during certain times during the study. Study participants There will be no restrictions regarding diet habits during the course of the study.

The SALI-10 lozenges and placebo lozenges will be pre-packed when given to each participant.

# 6.3 Telephone Pre-Screening

Potential study participants who contact the clinical trial coordinator for more information about the study via email will then be contacted via telephone. At this stage the Recruitment Questionnaire (Appendix 3) will be completed to determine whether they are eligible for the screening phase of the study. If the study participant is eligible for the study the screening visit will be scheduled.

#### **6.4 In-Person Screening**

Before any participant screening takes place, they will be given the Informed Consent Form to read and ask any questions they may have and sign. If signed, the remainder of the visit entails completion of the Personal Information Form (Appendix 4), and the Health Questionnaire form

(Appendix 5) and completion of an oral exam of both the soft and hard tissues (Screening Oral Assessment Form – Appendix 6). Female participants will be asked to take a urine pregnancy test. This is done to determine if the study participant is eligible for the study. The study personnel will then complete the screening form (hard copy).. The screening will be carried out until sixty (60) study participants are enrolled.

# 6.5 Pre-Induction Phase (Health Baseline – Study participant maintain dental hygiene at home for 14 days)

# 6.5.1 Visit 1 (t-2) Day -14

Study participants will undergo an oral hard and soft tissue exam as well as measurements of probing depth (PD), attachment level (AL), visible plaque index (VPI), gingival index (GI) and bleeding on probing (BOP) and recorded on the Oral Assessment Form (Appendix 7). The biospecimens collection will include gingival crevicular fluid (GCF), sub-gingival plaque, saliva and a saline oral rinse. All study participants will receive a prophylaxis (cleaning) which involves scaling and polishing to remove all supra- and subgingival plaque and calculus. Study participants will receive their assigned study product for use at home with directions. The participants will take two lozenges daily, one after their morning brushing and one after evening brushing. They will allow the lozenges to dissolve without biting or swallowing and avoid eating and drinking for one hour. The participants will be instructed on proper oral hygiene and will be instructed to continue their home oral hygiene in addition to use of their assigned product for 14 days (2 weeks). The participants will be instructed to return the lozenges' containers at each visit for protocol compliance check. Researchers will query participants on their use of NHPs, as well as any adverse effects they experienced.

#### 6.5.2 Visit 2 (t-1) (Day -7)

The study participants will return the containers containing the lozenges to a member of the study team. Study participants will then undergo an oral hard and soft tissue exam as well as measurements of probing depth (PD), attachment level (AL), visible plaque index (VPI), gingival index (GI) and bleeding on probing (BOP) and recorded on the Oral Assessment Form (Appendix 7). The biospecimen collection will include gingival crevicular fluid (GCF), plaque, saliva and a saline oral rinse. Researchers will query participants on their use of NHPs, as well as any adverse effects they experienced.

# 6.6 Induction Phase (No Oral Hygiene – for 21 days)

# 6.6.1 Visit 3 (t0) (Day 0)

The study participants will return the containers containing the lozenges to a member of the study team. Study participants will then undergo an oral hard and soft tissue exam as well as measurements of probing depth (PD), attachment level (AL), visible plaque index (VPI), gingival index (GI) and bleeding on probing (BOP) and recorded on the Oral Assessment Form (Appendix 7). The biospecimen collection will include gingival crevicular fluid (GCF), plaque, saliva and a saline oral rinse. Additionally, study participants will be asked to refrain from any oral hygiene for 21 days and to continue using the lozenges they were assigned, one during the morning, and one during the evening. Researchers will query participants on their use of NHPs, as well as any adverse effects they experienced.

# 6.6.2 Visit 4 (t1) (Day 7)

The study participants will return the containers containing the lozenges to a member of the study team. Study participants will then undergo an oral hard and soft tissue exam as well as measurements of probing depth (PD), attachment level (AL), visible plaque index (VPI), gingival index (GI) and bleeding on probing (BOP) and recorded on the Oral Assessment Form (Appendix 7). The biospecimen collection will include gingival crevicular fluid (GCF), plaque, saliva and a saline oral rinse. The participants will again be reminded to refrain from all forms of oral hygiene. Researchers will query participants on their use of NHPs, as well as any adverse effects they experienced.

# 6.6.3 Visit 5 (t2) (Day 14)

The study participants will return the containers containing the lozenges to a member of the study team. Study participants will then undergo an oral hard and soft tissue exam as well as measurements of probing depth (PD), attachment level (AL), visible plaque index (VPI), gingival index (GI) and bleeding on probing (BOP) and recorded on the Oral Assessment Form (Appendix 7). The biospecimen collection will include gingival crevicular fluid (GCF), plaque, saliva and a saline oral rinse. The participants will again be reminded to refrain from all forms of oral hygiene. Researchers will query participants on their use of NHPs, as well as any adverse effects they experienced.

# 6.7 Resolution (Study participants resume to regular dental hygiene home care for the rest of the study)

# 6.7.1 Visit 6 (t3) (Day 21)

The study participants will return the containers containing the lozenges to a member of the study team. Study participants will then undergo an oral hard and soft tissue exam as well as measurements of probing depth (PD), attachment level (AL), visible plaque index (VPI), gingival index (GI) and bleeding on probing (BOP) and recorded on the Oral Assessment Form (Appendix 7). The biospecimen collection will include gingival crevicular fluid (GCF), plaque, saliva and a saline oral rinse. All study participants will receive a prophylaxis (cleaning) which involves scaling and polishing to remove all supra- and subgingival plaque and calculus. The study participants will be instructed to continue using the lozenges they were assigned and resume home oral hygiene for the next 14 days (2 weeks). Researchers will query participants on their use of NHPs, as well as any adverse effects they experienced.

#### 6.7.2 Visit 7 (t4) (Day 28)

[figure not shown]
The study participants will return the containers containing the lozenges to a member of the study team. Study participants will then undergo an oral hard and soft tissue exam as well as measurements of probing depth (PD), attachment level (AL), visible plaque index (VPI), gingival index (GI) and bleeding on probing (BOP) and recorded on the Oral Assessment Form (Appendix 7). The biospecimen collection will include gingival crevicular fluid (GCF), plaque, saliva and a saline oral rinse. The study participants will be reminded to continue at home oral hygiene. Researchers will query participants on their use of NHPs, as well as any adverse effects they experienced.

# 6.7.3 Visit 8 End of Study (t5) (Day 35)

The study participants will return the containers containing the lozenges to a member of the study team. Study participants will then undergo an oral hard and soft tissue exam as well as measurements of probing depth (PD), attachment level (AL), visible plaque index (VPI), gingival index (GI) and bleeding on probing (BOP) and recorded on the Oral Assessment Form (Appendix 7). The biospecimen collection will include gingival crevicular fluid (GCF), plaque, saliva and a saline oral rinse. The study participants will be informed that this is the end of the study. They will be given their compensation and told that they may resume their regular oral hygiene. Once the study has been completed, the manufacturer will reveal to which group was the probiotic assigned to (either A or B). Afterwards, the investigators will inform participants to which group they were assigned and will ask for their feedback in regards to their experience. Researchers will query participants on their use of NHPs, as well as any adverse effects they experienced.

Please refer to figure 1. Illustrating the breakdown and timeline of the study as well as the relevant study procedures at each time point and the objectives.

Figure 1. Study Flow Infographic

#### 7. STUDY PROCEDURES AND CLINICAL REGISTRATIONS

Dental caries

S. mutans

S. sobrinus

B. dentium

C. albicans

#### 7.1 Abbreviated periodontal health assessment.

Respiratory diseases

S. pyogenes

S. agalactiae

S. pneumoniae

Clinical data will be documented based on probing depth (PD), attachment level (AL), visible plaque index (VPI), gingival index (GI) and bleeding on probing (BOP). All clinical measurements will be conducted using a manual periodontal probe.

**Halitosis** 

Actinomyces

Bacteroides

Eubacterium

Selenomonas

Solobacterium

Peptostreptococcus

S. salivarius

Rothia

Neisseria

Haemophilus

S. parasanguinis

www.ostiasciences.ca

#### 7.2 Gingival Bleeding Index

Periodontal diseases

P. gingivalis

T. forsythia

T. denticola

P. intermedia

F. nucleatum

Prepared by: [name], A. 2024

A. actimycetemcomitans

Bleeding on Probing (BOP): Absence or presence of bleeding after gentle probing will be recorded within 20 seconds of probing. All six sites of the all the teeth will be probed to determine BOP.

# 7.3 Visible Plaque Index

The surfaces of the study teeth will be scored and given either a "0" no plaque or "1" plaque assessment: 0 = No plaque; 1 = Visible Plaque

# 7.4 Loe and Silness Gingival Index (GI)

The surfaces of the study teeth will be evaluated using light air and a periodontal probe. A score is given based on the following scale: 0 = Normal gingiva; 1 = Mild inflammation, a slight change in colour, slight edema, no bleeding on probing; 2 = Moderate inflammation, moderate glazing, redness, bleeding on probing; 3 = Severe inflammation, marked redness and hypertrophy, ulceration, a tendency to spontaneous bleeding.

#### 7.5 Gingival Crevicular Fluid (GCF) Samples

Before GCF collection, the plaque index will be recorded. The sites to be sampled will be isolated with cotton rolls and gently air-dried. GCF samples will be collected with sterile paper strips (Periopaper strips, Oraflow Inc.) that will be inserted into the gingival crevice until mild resistance is felt and left in place for 30 seconds. GCF will be collected from the mesiobuccal and mesiopalatal surfaces of teeth (#'s 3, 4, 5, 12, 13, 14). Paper strips visibly contaminated with saliva and blood will be excluded from the study. All samples will be collected in microcentrifuge tubes. They will be transported on ice and stored within 24 hours at -80°C until processing. At our lab at Dental Sciences building, at University of Toronto, Faculty of Dentistry, these samples will undergo 40-plex chemokine analysis, oral neutrophil count and targeted proteomics

